5.4. Patient Recruitment

Patient authorization and written informed consent must be obtained prior to the patient's enrollment into the study and in accordance with GCPs, the Medical Devices Directive and all other applicable standards, regulations (local and national), guidelines and institutional policies.

The investigator(s) will verify each patient's inclusion/exclusion criteria before inclusion in the study. Selection criteria and completion of informed consent will be indicated on the Case Report Form.

All patients who sign a consent form will be assigned a study identification number. The identification number will be formatted using the abbreviation for the country, site identification number – sequential site recruited patient number (i.e. DE-005-004). Any patient meeting the study inclusion criteria, for whom this device is clinically indicated, can be recruited for the study after receiving and documenting informed consent.

5.5. Patient Screening and Suitability for C-Pulse Therapy

Patients diagnosed with moderate to severe heart failure and who are treated at the participating centers are eligible for screening evaluation.

Patients eligible for device implantation must meet all the inclusion and not meet the exclusion criteria (indications and contraindications based on device CE mark authorization and Instructions for Use). In addition, a screening process will be carried out for the objective of selecting ideal candidates for the C-Pulse System. Patient suitability will be evaluated in agreement between the Investigator and Sponsor.

Patients with one or more of the following conditions may be considered unsuitable for implantation of the C-Pulse system.

With regards to the severity of heart failure, patients with the following conditions may be unsuitable for implantation:

1. Inotrope dependence – inability to wean from inotropic therapy
2. ACC/AHA Stage D heart failure or non-ambulatory NYHA Class IV subject
3. Need for biventricular support
4. Functional limitation due to heart failure as defined by a 6 Minute Walk test of ≤ 175 meters, measured within 30 days prior to implantation

5. Need for concomitant cardiac surgery

Patients with the following cardiac conditions may also be excluded based on clinical judgment:

1. Hypertrophic obstructive cardiomyopathy, restrictive cardiomyopathy, pericardial disease, amyloidosis, active myocarditis, diastolic heart failure or technically challenging congenital heart disease
2. Reversible cause of heart failure that may be remedied by conventional surgery or other intervention
3. Cardiac surgery within 90 days prior to implantation
4. Prior cardiac transplantation, left ventricular reduction surgery, passive restraint device or surgically implanted left ventricular assist device

In addition, patients with severe co-morbidity may be excluded according to the judgment of the investigator. Condition of exclusion may include the following:

1. Body Mass Index (BMI) < 18 or > 45 kg/m²
2. Serum creatinine ≥ 2.5mg/dL or any form of dialysis within 30 days prior to the planned implantation
3. Evidence of intrinsic hepatic disease as defined as biopsy proven liver cirrhosis; or liver enzyme values (AST, ALT or total bilirubin) that are > 3 times the upper limit of normal within 30 days prior to enrollment
4. Patient has severe intrinsic pulmonary disease in judgment of the investigator
5. Stroke or transient ischemic attack (TIA) within 30 days prior to the planned implantation; or > 80% carotid stenosis as determined by carotid Doppler ultrasound
6. ST elevation myocardial infarction (STEMI) within 30 days
7. Uncontrolled atrial fibrillation or other tachycardias
8. Patient has a condition, other than heart failure, which would limit survival to less than 2 years
9. Patient demonstrates compliance issues that in the opinion of the investigator could interfere with the ability to manage the therapy (i.e. uncontrolled diabetes, mental health issues, etc.)
10. Positive serum pregnancy test, for women of childbearing potential

5.6. Schedule of Assessments

The study will aim to collect patient data while supported with C-Pulse therapy (i.e. the subjects will be censored from analysis if the device is permanently "off"). Data will be captured at the following time points: Baseline, procedure, discharge assessment, clinical follow-up at 6 weeks, 6 months, 12 months, 18 months, 2 years and yearly thereafter. Data from any other additional time points may be collected and analyzed if available.

The treatment procedure will be performed according to the instructions outlined in the current approved IFU. The data will be recorded from baseline and during a 5 year follow-up period following the enrollment. Treatments will be performed according to standard hospital practices. The clinical assessments will be done as per routine practice at the participating institutions.

The clinical variables of interest are presented in **Table 8** below. Hemodynamic performance and functional testing will be determined according to procedures based on standard center practices. Any protocol-defined adverse events, including adverse device effects and outcomes will be reported by the Investigator. All available variables of interest, that will be collected by the investigators, will also be recorded in the Study electronic CRFs.

Table 3 .Data Collection Summary.

	Pre-Implant (Baseline)	Implant	Pre-Discharge ²	6 week	6, 18 month	Annually ¹ Yr 1-5
PATIENT ELIGIBILITY	X					
GENERAL						
Demographic Data	X					
Medical History	X					
General Physical Exam	X	X	X	X	X	X
Concurrent Cardiac Meds	X	X	X	X	X	X
Weight (Height at enrollment)	X		X	X	X	X
Pregnancy test (if applicable)	X					
VITAL PARAMETERS						
Heart rate/rhythm	X		X	X	X	X
Blood pressure	X		X	X	X	X
Respiration rate	X		X	X	X	X
CARDIOPULMONARY³						
ECHO	X				X	X
6MWT	X			X	X	X
QUALITY OF LIFE						
INTERMACS™/NYHA Classification	X			X	X	X
KCCQ	X				X	X
HEMATOLOGY						
Hemoglobin	X		X		X	X
Hematocrit	X		X		X	X
Platelet count	X		X		X	X
White cell count	X		X		X	X
C-reactive Protein	X		X		X	X
BIOCHEMISTRY						
Serum sodium	X		X		X	X
Serum potassium	X		X		X	X
Serum creatinine	X		X		X	X
BUN	X		X		X	X
NTProBNP or BNP ⁴	X				X	X
Serum bilirubin	X		X		X	X
Serum ALT	X		X		X	X
Serum AST/GGT	X		X		X	X
IMPLANT DETAILS		X				
DEVICE LOG		X			X	X
DISCHARGE CHECKLIST			X			
ADVERSE EVENTS	X	X	X	X	X	X
DATA FROM THE FOLLOWING ITEMS WILL BE COLLECTED IF COMPLETED UPON PHYSICIAN REQUEST:						
MVO2	X					X
Right Heart Catheterization	X					X

¹ Annually post-implant for years 2-5

² At Discharge - within 36 hours prior and as close to discharge as possible

³ Imaging within 90 days prior to implant may be included as Baseline data collection

⁴ Complete NTProBNP or BNP consistently to the institution's standard practice (i.e. if BNP collected at baseline, continue BNP in scheduled follow-up)

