4. C-PULSE SYSTEM STUDY RATIONALE

4.1 Study Classification

The Sunshine Heart's C-Pulse® System is CE marked under Active Implantable Medical Devices Directive 90/385/CEE.

Based on European legislation, this post-market Study is considered to be an observational study. The following rationale supports this consideration:

- This study is collecting the data of subjects treated with the study product - C-Pulse® System in the usual manner and in accordance with the CE mark authorization.
- The assignment of the patient to this study is not decided by this study plan but falls within the current practice, and the treatment decision is separated from the decision to include the patient in this study.
- As the C-Pulse implantation procedure is clinically indicated patients may be enrolled prospectively with informed consent obtained prior to the procedure or retrospectively with informed consent for the collection of the patient's data obtained after the procedure as appropriate for an observational study. Standard diagnostic or monitoring procedures are applied to the treated patients. Available data will be collected in a central database.

The purpose of this observational surveillance study is to monitor the safety and performance of the C-Pulse System in the intended use population and confirm the favorable results obtained in premarket clinical investigations, which are summarized below.

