6.3. Performance Endpoints

The following performance endpoints will be assessed during follow-up visits:

- Improvement in INTERMACS™ and/or NYHA functional class
- Freedom from worsening heart failure resulting in hospitalization, LVAD implantation, or death
- Explant for recovery of ventricular function or cardiac transplantation

Secondary endpoints assessed at 6 and 12 months post implant include:

- Improvement in LVEF
- Improvement in Quality of Life scores
- Improvement in 6MWT

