6.5. Statistical Methodology

The sample size for the European protocol (N= 50 patients) was calculated on the basis of preliminary discussions with the Scientific Advisors of Sunshine Heart, and predicted success and safety rates observed in the literature data. Consistent design, procedures and endpoints of this study, as compared with the US trial, may allow pooling of data and comparative analyses. Demographic and baseline data will be summarized using descriptive statistics, including %, mean, median, standard deviation, and 1st-3rd quartile, as appropriate. The performance and safety endpoints of the C-Pulse® System will be assessed by monitoring the patient clinical status, assessing the standard quality-of-life scores, and evaluating vital, cardiopulmonary, hematology, biochemistry and neurological parameters, cardiopulmonary test data during the visits within the follow-up period, as detailed in the Data Collection Summary shown in Table 8. Follow-up analysis will include both safety and performance analyses, at each of the defined intervals. Adverse event data will be summarized using descriptive statistics. These will include information concerning nature, severity and duration of all adverse events and their relationship to the different treatments. In addition, tables will be presented for the number of patients potentially available for follow-up and those actually followed. Reference rates for anticipated complications (adverse events), based on historical data on morbidity and mortality from previous device clinical experience, in similar populations and for analogous surgical procedures, are listed in the Literature Review. Overall mortality rate will be determined at the end of the study.

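### Improvement in LVEF, KCCQ and 6MWT at 6 and 12 months has no stated denominator or rule for death, LVAD, transplant or missed tests, so the figures would cover only patients alive, on the device and tested

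*Combined protocol and SAP*

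**What the plan says.** Section 6.3 introduces the secondary endpoints with "Secondary endpoints assessed at 6 and 12 months post implant include" and lists LVEF, quality-of-life scores and the walk test. Each is worded like the last, "Improvement in 6MWT", with no threshold. KCCQ is the quality-of-life instrument in Table 3.

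On data collection, Section 5.6 states that "The clinical assessments will be done as per routine practice at the participating institutions". It adds "Hemodynamic performance and functional testing will be determined according to procedures based on standard center practices", and then "All available variables of interest, that will be collected by the investigators, will also be recorded in the Study electronic CRFs". Section 4.1 agrees: "Standard diagnostic or monitoring procedures are applied to the treated patients. Available data will be collected in a central database".

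Section 5.6 also takes a patient out of the analysis once the device is permanently off, with no exception. The synopsis (Data collection row) states the same rule but exempts patients whose device is off because of signs of recovery.

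On analysis, Section 6.5 says "Follow-up analysis will include both safety and performance analyses, at each of the defined intervals". It promises descriptive summaries and counts of patients who could have been followed and who were. Section 7.3 allows data gathered before loss to follow-up to be used. No section gives a denominator, a missing-data method, or a way of counting death, LVAD, transplant or an untested patient in the secondary endpoints.

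**The concern.** Section 4.1 gives the purpose as monitoring the device and confirming the good premarket results. The Clinical Risk/Benefit Assessment in Section 4 names quality of life, ejection fraction and the six-minute walk among those results. The secondary endpoints therefore carry much of the benefit claim.

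A patient who has died, or whose device is permanently off, cannot contribute a 12-month value under the plan as written. A patient too ill to walk will not have a walk distance. If the patients who drop out of the figure are mainly those doing badly, the mean change or proportion improved among the rest rises even when the device does nothing. There is no control arm to show the same drift, so selective loss would read as benefit.

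**Working it through.** **Step 1. The plan's own figure.** Section 6.6 justifies 50 patients by the width of 95% confidence intervals. The readable text has neither the reference rates nor a target width, so 50 cannot be re-derived. The precision it implies can be computed. At 40%, the premarket exit-site infection rate in Section 4.3, the half-width is 1.96 × √(0.4 × 0.6 / 50) = 0.136, or ±13.6 points. For a mean change the half-width is t(0.975, n−1)/√n in SD units: 0.284 SD with 50 assessed and 0.344 SD with 35. The loss of precision from missing tests is modest. The issue is which patients are missing.

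**Step 2. How far the observed rate can sit from the all-implanted rate.** N = 50 comes from Section 6.6; every other input is assumed. Let D be dead or on LVAD (counted as not improved), U alive but untested, T = N − D − U tested, and x improved. The observed rate is x/T, the worst case x/N and the best case (x + U)/N.

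| D | U | T | x | Observed | Worst case | Best case |
|---|---|---|---|---|---|---|
| 8 | 12 | 30 | 20 | 20/30 = 67% | 20/50 = 40% | 32/50 = 64% |
| 6 | 14 | 30 | 20 | 20/30 = 67% | 20/50 = 40% | 34/50 = 68% |

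With x = 20 and T = 30, the best case falls below the observed rate only if (20 + U)/50 < 20/30, that is, U of 13 or fewer. The worst case is below the observed rate in both rows.

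A second range takes 60% improved among those tested and lets every missing patient count either way:

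| Missing | Improved/tested | Worst case | Best case |
|---|---|---|---|
| 10% | 27/45 | 27/50 = 54% | 32/50 = 64% |
| 20% | 24/40 | 24/50 = 48% | 34/50 = 68% |
| 30% | 21/35 | 21/50 = 42% | 36/50 = 72% |
| 40% | 18/30 | 18/50 = 36% | 38/50 = 76% |

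**Step 3. What selective loss does when the true mean change is zero.** Suppose the worst share m on a latent health score goes unmeasured, and that score has correlation ρ with the change. The expected upward bias in the observed mean is ρ·φ(z)/(1 − m), with z the 1 − m normal quantile. For m = 0.2 and ρ = 0.5 this is 0.5 × 0.280/0.8 = 0.175 SD. In 20,000 simulated cohorts of 50:

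| m | ρ | Simulated bias (SD) | Rejections by a two-sided 5% t-test |
|---|---|---|---|
| 20% | 0.3 | 0.10 | 10% |
| 20% | 0.5 | 0.17 | 21% |
| 20% | 0.7 | 0.24 | 39% |
| 30% | 0.3 | 0.15 | 15% |
| 30% | 0.5 | 0.24 | 32% |
| 30% | 0.7 | 0.34 | 61% |

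With ρ = 0 there is no bias and rejection stays near 5%. The t-test is only a yardstick; the plan specifies none. The values of m and ρ are assumptions.

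**The case against.** The case on the other side has real content.

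- **The tests are scheduled.** Table 3 marks echo, 6MWT and KCCQ at baseline, at 6 and 18 months and annually. Only MVO2 and right heart catheterization depend on the physician's request, and Section 7.7 has monitoring for complete data. A reader might infer that the three tests are collected only if a site happens to do them. Table 3 does not support that. But perfect attendance would still leave out deaths and device-off patients.
- **Observed-case analysis is never stated.** A reader might take it as the declared method. It is not: it is the default when only available data are recorded and no other rule is given.
- **Restriction to time on the device is declared.** The synopsis and Section 5.6 say the study aims to collect data during support. That is a legitimate choice for a descriptive study, and it should remain as a supportive result. It answers a narrower question than how implanted patients fare.
- **Bad outcomes are reported elsewhere.** Section 6.3 has an endpoint covering heart-failure hospitalization, LVAD and death, Section 6.4 has mortality, and 6.5 tabulates follow-up. This makes attrition visible but does not alter the improvement figures or record why a test was missed.
- **The direction is not certain.** Section 5.6 as written also removes patients whose device is off for recovery, which pulls the other way. Being too ill to walk bears on the 6MWT and need not prevent a questionnaire or an echo.

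**Conclusion.** The gap is real, and it goes beyond missing detail: the device-off rule and the recording of available data, followed as written, produce improvement figures for patients alive, on the device and tested. In a single-arm study meant to confirm premarket benefit, that probably flatters the device. This rests on the assumption that sicker patients are the ones unmeasured, which the documents do not quantify.

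The size is unknown, since no missingness or mortality rate is given. The 67% against 40% to 64% comparison is illustration only. A reader might infer from it that even the most favourable all-implanted rate must fall below the observed one. That does not hold in general: 6 dead or on LVAD and 14 untested give a best case of 68%. Nor do the documents support a claim about false-positive findings, since no hypothesis test is planned.

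Because these are secondary, descriptive endpoints, the plan should be changed on this point, but the study does not stand or fall by it.

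**What to change.** In Section 6.5, for each secondary endpoint at 6 and 12 months:

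1. Also report the proportion improved among all implanted, consented patients. Consent has to be part of the denominator because Section 5.2 allows it after implantation. Fix the threshold for improvement before the data are reviewed.
2. Count death, LVAD and, for the 6MWT, inability to walk because of illness as not improved.
3. State in advance how transplant and device-off patients are counted, keeping device off for recovery separate from device off for other reasons. Transplant needs an explicit rule because Section 6.3 lists explant for recovery or transplantation as a performance endpoint without saying which way it counts.
4. Show worst- and best-case bounds for the other missing tests.
5. Keep the observed-case mean change as supportive, with the number assessed.

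Add one e-CRF field for the reason a test was not done. Reconcile the synopsis with Section 5.6 on the recovery exception to censoring. Reconcile the Table 3 column header (years 1 to 5) with its footnote 1 (years 2 to 5), so that it is clear the 12-month tests are scheduled.

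The cost is a paragraph in 6.5, one e-CRF field and slightly more analysis work. No test becomes mandatory, so the observational status is unaffected. The downside for the sponsor is lower stated response rates.

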6. STUDY DESIGN AND OBJECTIVES

6.1. Study Objective

This is a multi-center, prospective, open label observational study, designed to observe the clinical outcomes of heart failure patients treated with the C-Pulse® System in the usual manner and according to the approved indications and contraindications.

6.2. Enrollment

A patient population of up to 50 patients with moderate to severe heart failure refractory to optimal medical therapy, who are implanted with the C-Pulse System as clinically appropriate, will be enrolled into the Study. A maximum of 15 European centers will participate. Study data from additional geographies may be included.

Patients diagnosed with moderate to severe heart failure and who are treated at the participating centers are eligible for screening evaluation. The investigator(s) will obtain informed consent for study participation from each patient.

Patients eligible for the study must meet all the inclusion criteria and not meet the exclusion criteria (indications and contraindications based on device CE mark authorization and Instructions for Use). In addition, a screening process will be carried out the objective of selecting ideal candidates for the C-Pulse System (see Section 5.5). Patients suitability will be evaluated in agreement between the Investigator and Sponsor, based on the assessment of heart failure severity, concomitant cardiac disease, need for concomitant cardiac surgery, co-morbidity, life expectancy < 2 years, pregnancy and other conditions potentially interfering with the ability to manage the C-Pulse therapy.

After implantation of the C-Pulse System, patients will be followed up for 5 years to collect performance and safety data.

The estimated time course of the study is as follows:

First Patient In: May 2013

Last Patient In: Dec 2014

Last Patient Out: Dec 2019

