Locations	A maximum of 15 European sites will participate. Study data from additional geographies may be included.
Estimated Time Course	First Patient In: May 2013 Last Patient In: Dec 2014 Last Patient Out: Dec 2019
Introduction	Pharmacological and device-based therapies for heart failure continue to be refined though still pose challenges. Now Sunshine Heart introduces the C-Pulse® System, designed to provide the well-known clinical benefits of counter-pulsation heart pumping support while allowing the patient to move and go back home, having a quite normal day-life style.
Technology	Sunshine Heart's C-Pulse® System is a new approach for patients with moderate to severe heart failure that can be used in combination with other heart failure therapies. The device is designed to assist the heart's function, not replace it and may be implanted using a minimally invasive approach. The C-Pulse® system is designed to provide an effective, low risk and low cost wearable mechanical heart assist device for use in patients in NYHA Class III-IV ambulatory. It is intended for use in hospital and at home.

Implantable C-Pulse Cuff.

External wearable components.

How does C-Pulse® System work?	
The C-Pulse® implanted cuff is wrapped around the ascending aorta and is pneumatically driven, via a percutaneous line, by an external driver. Inflation and deflation are timed from the ECG, sensed via an epicardial lead that is connected to the percutaneous interface lead.
 
The C-Pulse® System is simple to implant and accommodates aortic anatomic variability. C-Pulse® System allows patient mobility and can be turned off or used intermittently if recovery occurs or for day-life exigencies. In addition, the C-Pulse cuff sits outside the bloodstream, therefore eliminating the need for anti-clotting medications.

Regulatory status	CE marked
Study objective	Evaluation of the post-market clinical performance and safety of the C-Pulse® System for the treatment of Heart Failure in the population of patients who meet the approved clinical conditions provided in the indications and contraindications.
Patient population	A patient population of up to 50 patients with moderate to severe heart failure refractory to optimal medical therapy, who are implanted with the C-Pulse System as clinically appropriate, will be enrolled into the Study.

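### A sponsor-agreed screen for ideal candidates sits under study eligibility, so results would describe a selected subset of the labelled population named in the objective

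*Combined protocol and SAP*

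**What the plan says.** **Target population.** The synopsis states the objective as performance and safety "in the population of patients who meet the approved clinical conditions provided in the indications and contraindications". Section 6.1 describes patients "treated with the C-Pulse® System in the usual manner and according to the approved indications and contraindications". Section 4.1 gives the purpose as to "monitor the safety and performance of the C-Pulse System in the intended use population".

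**Inclusion by label.** Section 4.1 supports the observational classification partly on the ground that "the treatment decision is separated from the decision to include the patient in this study". Section 5.4 allows recruitment of any patient who meets the inclusion criteria and for whom the device is indicated. Section 7.2 bases enrolment on the approved labelling.

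**The added step.** Section 6.2 lists the label criteria as conditions for study eligibility and then says that, in addition, "a screening process will be carried out the objective of selecting ideal candidates for the C-Pulse System (see Section 5.5". It continues: "Patients suitability will be evaluated in agreement between the Investigator and Sponsor". The synopsis (Screening process) and Section 5.5 carry the same step; 5.5 says "Patient suitability will be evaluated in agreement between the Investigator and Sponsor". Section 5.5 then lists heart-failure, cardiac and co-morbidity conditions, for example "Patient has a condition, other than heart failure, which would limit survival to less than 2 years".

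**Timing.** The synopsis and Sections 4.1 and 5.2 allow a patient to be enrolled after the implant, with consent to data collection obtained then.

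**The concern.** A post-market study that aims to describe a device in its labelled population needs entry to depend on the label and on consent. Here the sponsor, whose stated purpose in 4.1 includes confirming favourable premarket results, takes part in deciding who is suitable. The conditions that guide this decision are related to outcome. A short six-minute walk (6MWT of 175 m or less) is one of them, and 6MWT is a secondary endpoint. Raised creatinine and limited non-cardiac survival bear on all-cause mortality, a primary safety endpoint.

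Two things are at stake. First, rates from the study may be read as those of all label-eligible patients when they come from a narrower group that the protocol does not define, because the conditions are discretionary. Second, for a patient already implanted, a suitability judgement made at enrolment could be made with early events in view.

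**Working it through.** **1. Passages side by side.** Section 5.4 (any indicated patient meeting the inclusion criteria) and Section 7.2 (enrolment on labelling) leave no room for a further condition of entry. Section 6.2 adds one. The synopsis and 5.5 attach the screen to eligibility for implantation, while 6.2 attaches it to eligibility for the study. The documents therefore do not settle whether the screen governs treatment, data collection or both. If it governs treatment and is run as part of the study, it conflicts with the separation claimed in 4.1. If it governs data collection, it conflicts with 5.4 and 7.2.

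**2. Counting the conditions in 5.5.** Heart-failure severity 5, cardiac 4, co-morbidity 10: 5 + 4 + 10 = 19. One of these (Stage D or non-ambulatory Class IV) is already outside the indication, so at most 19 − 1 = 18 narrow the labelled population. All three lists are worded as what may lead to exclusion.

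**3. Patients already implanted.** Several 5.5 time windows run back from the implantation, which suggests a pre-implant screen. Section 6.2 has no such limit and no exemption for retrospective enrolment.

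**4. Visibility of the selection.** Section 6.5 plans one denominator table, for follow-up. Section 5.4 numbers every patient who consents, and 7.5 asks sites to keep enrolment logs. No section requires label-eligible patients who were declined to be recorded with reasons or reported.

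**5. Possible size.** The plan gives no figure for the effect of selection, so there is none to reproduce. Let s be the share of label-eligible patients screened out, p_in the event rate in selected patients and p_out the rate in those screened out. Then:

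- labelled-population rate = (1 − s) × p_in + s × p_out
- bias of the study rate = −s × (p_out − p_in)

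N = 50 and the two-sided 5% level come from Section 6.6. The values of s, p_in and p_out are **assumed**. With p_in = 20%, the 95% half-width is 1.96 × √(0.20 × 0.80 / 50) = 11.1 points.

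| s | p_out / p_in | p_out | Labelled rate | Bias (points) | Approx. coverage of labelled rate by the 95% CI |
|---|---|---|---|---|---|
| any | 1.0 | 20% | 20% | 0 | 95% |
| 10% | 1.5 | 30% | 0.9 × 20 + 0.1 × 30 = 21% | −1 | 95% |
| 30% | 2.0 | 40% | 0.7 × 20 + 0.3 × 40 = 26% | −6 | 81% |
| 50% | 2.0 | 40% | 0.5 × 20 + 0.5 × 40 = 30% | −10 | 58% |

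Under these assumptions the effect runs from nothing to about the size of the confidence half-width. Nothing in the documents places the study within that range.

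**The case against.** The strongest reply is that Sections 5.1 and 6.1 speak of patients treated with the device. A patient declined before implant has no device outcome to observe, so the study still describes what it sets out to describe. This stands in part. A reader might infer that the study cannot answer its objective; the documents do not support that. It can describe treated patients within the label. What is limited is the extension to everyone who meets the label, which the synopsis wording invites.

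A reader might also take the 19 conditions as 19 further entry requirements. They are not: each is discretionary, and at least one repeats the indication. What is stated as something that will happen is the joint evaluation. Discretion does not remove the difficulty, because the selected population then cannot be defined from the protocol.

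A third inference is that the sponsor holds a veto and will use it on known outcomes. The text says only that suitability is evaluated in agreement, and 5.5 is framed around implantation. What stands is an unclosed gap in 6.2, not evidence of selection on outcome.

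Finally, the screen is openly disclosed, and Section 7.10 plans only a descriptive report, so it is a prediction that the results will be presented as those of the labelled population. That is fair. But nothing limits the conclusion to selected candidates either.

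**Conclusion.** The concern holds as an inconsistency with consequences for bias and generalisability. Sponsor-agreed selection in 5.5 and 6.2 conflicts with the labelled-population objective and with the inclusion rules in 4.1, 5.4 and 7.2. The results would apply to a selected subset and would probably look favourable for the labelled population. The direction rests on the listed conditions being mostly markers of worse prognosis. The size cannot be estimated from the documents, and the range shown above rests on assumed inputs that include no effect at all. Without a record of declined patients, the study's own data would not supply those inputs. The route most worth closing is a suitability judgement on patients already implanted, because there the early outcome may be known.

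**What to change.** Reconcile Sections 4.1, 5.4 and 7.2 with 5.5 and 6.2.

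- In 6.2, make every consenting patient implanted within the label at a participating site eligible for data collection. State that sponsor agreement on suitability is not a condition of study entry, in particular for patients already implanted.
- This alone does not undo selection made before implant. So record each 5.5 condition present before implant as a baseline variable, and keep and report a log of label-eligible patients declined, with reasons. The enrolment log in 7.5 could be extended for this.
- Where the screen is kept, limit the objective and the final-report conclusion to selected candidates within the label.

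The cost is protocol wording, a short checklist of conditions and a log. The sponsor may have to accept a narrower claim or less favourable rates. No change is proposed to how sites choose patients for implant, and no view is taken on which 5.5 conditions are right.
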